Study Protocol and Statistical Analysis Plan

Modulation of the Intestinal Microbiome by a High Protein Diet

NCT04812964

Document date: April 5, 2018

STUDY PROTOCOL: Modulation of the Intestinal Microbiome by a High Protein Diet

A. Design of randomized, controlled study comparing high and normal protein isocaloric calorie restriction diets for obesity.

Rationale and hypothesis: Based on my preclinical rodent model data, I hypothesize that a high protein diet will shift the composition of the microbiome of obese subjects, including increased *Akkermansia*, and that this will be associated with alterations of the metagenome (bacterial genes) and metabolome.

Study design: This hypothesis will be investigated in a randomized controlled study of the intestinal microbiome of an estimated 216 obese Veterans assigned 1:1 to isocaloric high protein (HPD) or normal protein (NPD) diets. The study will be advertised by posting flyers in the West Los Angeles VA Medical Center MOVE obesity clinic. MOVE physicians will provide interested patients with information about the study. Participants will undergo an initial screening visit in the clinical research unit after their MOVE appointment or on a later date. Once enrolled, participants will return to the clinical research unit for a baseline visit and follow-up visits on weeks 2, 4, 6, 8, 12, and 16 for dietary counseling, physical measurements, phlebotomy, and dietary questionnaires. The recruitment rate is estimated as 7 per month based on the recently completed study led by [name]. Patient recruitment and sample collection will be performed during the first 3 years of the study.

Inclusion criteria: Men and women between 20 and 75 years of age, BMI 27 to 40 kg/m², non-smoker or stable smoking habits for at least 6 months prior to screening and agreement not to change such habits during the study; subjects on non-obesity prescription medication may be included.

Exclusion criteria: Weight change of > 3.0 kg in the month prior to screening, weight loss of > 10 kg in the 6 months prior to screening, calorie restriction diet (< 1500 kcal/day) for a period of 4 months or more in the 12 months prior to screening, use of any other investigational drug(s) within 8 weeks prior to screening, abnormal baseline laboratory parameters (serum creatinine > 1.6 mg/dl; ALT, AST, total bilirubin > 2.0 times the upper limit of normal; triglycerides > 500 mg/dl, total cholesterol > 350 mg/dl, TSH outside of normal range), consumption of more than 1 alcoholic beverage per day, pregnancy or intention to become pregnant.

Consent: Veterans will be consented during their screening visit. They must sign the VA GLAHS Institutional Review Board-approved written informed consent prior to the initiation of any study specific procedures or randomization.

Enrollment and randomization: Date of birth, sex, race, medical history, current medications, smoking and alcohol history will be obtained by the study coordinator during the screening visit. Eligible subjects will be assigned an enrollment number after signing the informed consent form then will be randomized to one of two diet groups.

Dietary intervention: Participants will be randomized to a HPD (30% protein, 40% carbohydrate, 30% fat) or a NPD (15% protein, 55% carbohydrate, 30% fat) with matched fatty acid profiles and fiber content. The diet will be implemented in two phases: an initial macronutrient standardized diet without calorie restriction for 2 weeks then the same macronutrient standardized diet with 1500 calorie restriction for 14 weeks. Subjects will receive dietary counseling during their baseline visit on their assigned macronutrient standardized diet. After 2 weeks of a macronutrient standardized diet, both groups will then receive further dietary counseling on how to restrict their intake to 1500 calories. Pea-based protein supplements will be provided to the HPD group to achieve the target of 30% calories from protein in the HPD group.

Nutritional assessments: Participants will complete a three-day food record (3DFR) and the Food Frequency Questionnaire (FFQ) at every study visit to assess adherence to the prescribed macronutrient composition and calorie limit of the two dietary groups. The 3DFR consists of detailed documentation of food eaten on three days. FFQ is a self-administered, semi-quantitative tool that queries the average frequency of consumption over the prior one month of a list of food items. It will be modified to cover only 2 weeks on study visits at weeks 2 and 4. This study will use the Diet History Questionnaire supported by the National Cancer Institute and previously validated against other FFQs. The extensive nutrient composition database that supports the questionnaire allows estimations of the intake of macronutrients (e.g. fats), micronutrients (e.g. carotenoids), and specific food groups such as fruits, vegetables and grains.

B. Measurement of clinical response to the dietary interventions.

Primary and secondary endpoints: The primary clinical endpoint for response to dietary intervention will be weight loss. Secondary measures of clinical response will include change in fat mass, liver steatosis, lipids, and HgbA1c.

Clinical data collection: The following parameters will be obtained on each of 7 study visits: baseline, week 2, week 4, week 6, week 8, week 12, and week 16.

- 1) Physical examination: The study coordinator will measure height, weight, and waist/hip circumference.
- 2) Bioelectrical impedance analysis (BIA): Electrodes attached to a BIA device will be placed on the wrists and ankles. A brief electrical current will be passed to measure resistance and reactance, which can be used to calculate lean body mass and fat mass. One BIA device will be dedicated to this study.
- 3) Liver transient elastography (FibroScan): Hepatic steatosis and fibrosis will be evaluated by transient elastography, a non-invasive test that can be performed in 5 minutes using equipment that will be available down the hall from the clinical research unit where study visits will occur. Steatosis will be assessed by the CAP score and fibrosis by elastography with stiffness measured in kilopascals.
- 4) Laboratory studies: Blood samples will be collected by venipuncture after 8-14 hours of fasting. Complete blood count, chemistry panel, lipids (total cholesterol, LDL, HDL, triglycerides), and hemoglobin A1c (HgbA1c) will be measured by the clinical laboratory at the West Los Angeles VA Medical Center.

Statistical analysis: Patient characteristics (physical measurements, lean body mass, laboratories, demographic traits) at baseline will be compared using a 2-sided t-test (for numerical variables) or chi-square test (for categorical variables) to evaluate the randomization. 3DFR and FFQ performed at each time point will be used to assess the predicted protein content of the patient's diet compared to baseline to evaluate the success of the dietary intervention. The significance of differences between the two groups in the primary and secondary outcome measures will be assessed using a 2-sided t-test.

C. Kinetic analysis of shifts in microbial composition in obese subjects (BMI 27-40) on a high protein diet compared to an isocaloric normal protein diet.

Fecal sampling: Participants will be provided with kits for home sampling. The subjects will urinate first then defecate into the Fisherbrand Commode Specimen Collection System. Subjects will use a spoon to transfer freshly defecated feces to a Para-Pak stool collection cup prefilled with 95% ethanol to fix the samples, allowing storage at room temperature for up to 2 weeks. Ethanol-fixed and fresh frozen samples give comparable metagenomics results to samples stored in preservatives such as RNALater while minimizing subjects' risk of exposure to toxic chemicals. The remaining feces will be frozen. This involves removing the cup from the

toilet hat, tightly closing the lid, and transferring the cup to a Ziploc bag for storage in the subject's freezer. Frozen samples will be delivered to the VA clinic during scheduled study visits using a Styrofoam box containing U-tek freezer packs designed to maintain a temperature of -20°C as was performed for a recent study. Reminder calls will be made 4 days before each study visit. Subjects who forget to bring in samples will be asked to either bring them in at the next visit or send them via overnight FedEx delivery. Samples will be stored at -80°C.

Microbiome analysis: DNA will be extracted from fecal samples collected in ethanol at baseline, day 3, day 7, week 2, day 17 (3 days after calorie restriction), day 21 (7 days after calorie restriction), week 4, week 6, week 8, week 12, and week 16 using the MO BIO Powersoil kit. Sequencing of the 253 base pair V4 region of 16S ribosomal DNA will be performed using the Illumina HiSeq 2500 to a depth of 250,000 reads per sample. Microbial diversity (alpha diversity) will be compared between the two dietary groups at each time point using the Chao1 index, Shannon index, and Faith's phylogenetic diversity. Significance will be determined using a non-parametric test (Mann-Whitney U). Microbial composition (beta diversity) will be compared across all samples using weighted UniFrac (a phylogenetic distance metric) and visualized by principal coordinates analysis (PCoA). Significance of differences in composition at each time point will be determined using Adonis, a permutation-based method. Baseline data will be analyzed to confirm that randomization had successfully eliminated pre-existing microbial differences between the two dietary groups.

Abundance of individual bacteria will then be fitted to multivariate models using DESeq2. This algorithm performs normalization using size factors estimated by the median-of-ratios method, employs an empirical Bayesian approach to shrink dispersion, and fits the data to negative binomial models. Diet group, time point, interaction between diet and time point, baseline BMI, age, sex, and smoking status will be covariates in the model. Diet composition parameters derived from the nutritional instruments (3DFR, FFQ) may also be included. This model will be compared to a reduced model that does not include the diet:time point interaction. A likelihood ratio test will be used to identify microbes with differential abundance by diet at time points after baseline. Estimates of significance will be adjusted for multiple hypothesis testing to calculate q-values, which represents the false discovery rate. Q-values less than 0.05 will be considered significant. Microbes that are differentially abundant on a HPD will be grouped by hierarchical clustering to highlight distinct kinetic patterns of microbial change.

D. Risk/benefit analysis

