1. RISKS TO SUBJECTS

a. Human subjects involvement and characteristics

Human subjects will be recruited from the MOVE Obesity Clinic at the West Los Angeles VA Medical Center within the VA Greater Los Angeles Healthcare System (GLAHS). They will be referred for study enrollment if they meet the inclusion criteria and do not meet any provisions of the exclusion criteria. The inclusion criteria include: men and women between 20 and 60 years of age, BMI 27 to 40 kg/m², non-smoker or stable smoking habits for at least 6 months prior to screening and agreement not to change such habits during the study. The exclusion criteria include weight change of > 3.0 kg in the month prior to screening, weight loss of > 10 kg in the 6 months prior to screening, calorie restriction diet (< 1500 kcal/day) for a period of 4 months or more in the 12 months prior to screening, use of any other investigational drug(s) within 8 weeks prior to screening, abnormal baseline laboratory parameters (serum creatinine > 1.6 mg/dl; ALT, AST, total bilirubin > 2.0 times the upper limit of normal; triglycerides > 500 mg/dl, total cholesterol > 350 mg/dl, TSH outside of normal range), consumption of more than 1 alcoholic beverage per day, pregnancy or intention to become pregnant. Following

informed consent, subjects will undergo randomization to either the normal protein diet or high protein diet groups. Both dietary interventions are consistent with clinical practice for management of obesity and do not pose any appreciable risk to the patient. Subjects will be asked to collect stool eleven times and to visit the VA clinical research unit seven times over 16 weeks.

b. Sources of material

Data and materials collected during the study will be used only according to the protocol approved by the VA Institutional Review Board (IRB). All information will be retained electronically behind the VA's electronic firewall except for regulatory documents and printed informed consent forms. All subjects will receive a unique research identifier number with the identities of the subjects retained only in a code key kept in a secure directory behind the firewall. Stool will be collected by techniques described in Aim 1 of the Research Plan. Demographic and medical data will be collected for all of the subjects according to the study protocol. Only the principal investigator (PI, [name]) and study coordinator will have access to confidential patient information.

c. Potential risks

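### The hypothesis predicts a rise in Akkermansia, but its only taxon-level test is an undirected diet-by-time screen that cannot show a rise

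*Combined protocol and SAP*

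**What the plan says.** Section A (Rationale and hypothesis) draws on rodent data to predict that the high protein diet "will shift the composition of the microbiome of obese subjects, including increased *Akkermansia". No other taxon is named anywhere in the document.

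Section C (Microbiome analysis) fits each bacterium with DESeq2. The terms are: "Diet group, time point, interaction between diet and time point, baseline BMI, age, sex, and smoking status will be covariates in the model". The test is then defined: "This model will be compared to a reduced model that does not include the diet:time point interaction". Its purpose is stated as follows: "A likelihood ratio test will be used to identify microbes with differential abundance by diet at time points after baseline". After adjustment for multiple testing, "Q-values less than 0.05 will be considered significant".

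Section D, item 1a, confirms the number of samples: "Subjects will be asked to collect stool eleven times". Section C lists the times: baseline, days 3 and 7, week 2, days 17 and 21, and weeks 4, 6, 8, 12 and 16.

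The other microbiome tests in section C are community-level: Mann-Whitney for alpha diversity and Adonis for weighted UniFrac composition. Hierarchical clustering is applied only to microbes already found to differ. The plan specifies no contrast, time point, direction, alpha level or effect size for Akkermansia.

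**The concern.** The prediction has a sign and one target. The test that would judge it has neither.

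A significant interaction says only that the difference between diets is not the same at all time points. A fall, a brief spike or an oscillation in Akkermansia could each give q < 0.05. Someone would then have to decide, after seeing the data, which of ten post-baseline times, or which average of them, counts as the increase.

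The q-value also ties the verdict on Akkermansia to the other taxa: how many are tested, and how many turn out to differ. Neither bears on the prior hypothesis.

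Power is a second issue. A test spread over many degrees of freedom is less sensitive to a simple sustained shift than a contrast aimed at that shift, and the false-discovery threshold adds to the loss. How much is lost depends on the time course, so it has to be worked out by case.

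**Working it through.** **The plan's own figure.** There is no power statement to reproduce. The sample size is given as "an estimated 216 obese Veterans assigned 1:1 to isocaloric high protein (HPD) or normal protein (NPD) diets", without effect size, SD, dropout or derivation. For scale only: with 108 per arm, no dropout and two-sided 0.05, a 1-df comparison has 80% power at a standardised difference of 0.381. That is the sense of "moderate" below.

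**Degrees of freedom.** With time point as a category, the interaction has (2 − 1) × (11 − 1) = 10 df. The plan does not state the df.

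**Threshold.** Under a Benjamini-Hochberg type rule, the per-taxon cut-off is about 0.05 × R/M, for R discoveries among M taxa. The plan gives neither number. If 10% of taxa are declared significant, the cut-off is 0.005; if 2%, it is 0.001. For M of 100 to 300 and R of 1 to 40, the range is about 0.00017 to 0.02.

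**Set-up (assumptions).** Equal variance and equal correlation across the 11 times, complete data, normal approximation, participant accounted for. In units where the independent part of each measurement has variance 1, the ten changes from baseline have covariance V = I + J (J is the matrix of ones). The arm-size factor is common to both tests and cancels. Let d be the vector of diet differences in change from baseline.

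- Contrast, the mean of weeks 4, 6, 8, 12 and 16 minus baseline: variance 1/5 + 1 = 1.2, so non-centrality = (mean of d over those weeks)² / 1.2.
- Interaction test: non-centrality = d′V⁻¹d = Σd² − (Σd)²/11, on 10 df.
- The contrast is set to 80% power at two-sided 0.05: non-centrality (1.960 + 0.842)² = 7.85. The interaction non-centrality is then 7.85 times the ratio of the two expressions.

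**Three time courses.**

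1. Constant from day 3: contrast 1/1.2 = 0.833; interaction 10 − 100/11 = 0.909; ratio 1.091; non-centrality 8.56.
2. Starting after day 14, then constant (7 of the 10 times): contrast 0.833; interaction 7 − 49/11 = 2.545; ratio 3.055; non-centrality 23.98.
3. Linear ramp to week 16 (d = day/112): contrast 0.575²/1.2 = 0.2755; interaction 2.0941 − 3.4286²/11 = 1.0254; ratio 3.722; non-centrality 29.21.

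Power of the 10-df test, from the non-central chi-square, when the contrast has 80%:

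| Time course | p < 0.05 | p < 0.005 | p < 0.001 |
|---|---|---|---|
| Constant from day 3 | 47% | 18% | 8% |
| Starts after day 14 | 95% | 79% | 63% |
| Linear ramp to week 16 | 98% | 90% | 79% |

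In the first row, the degrees of freedom alone take power from 80% to 47%. The loss exceeds half only once a false-discovery cut-off is applied: at p < 0.01 the figure is 24%. In the other two rows the early samples act as extra baseline. The interaction test uses them and the contrast does not.

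**Check against a perfectly matched contrast.** If the 1-df contrast fits the true time course exactly, both tests share non-centrality 7.85, and the 10-df test has 43%, 15% and 7% at the same three cut-offs. That is a reference case, not the performance of the weeks 4 to 16 contrast.

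**The case against.** The strongest defence is that section C is framed as a study of kinetics. Stool is sampled densely around both diet changes, and an omnibus diet-by-time test suits a time course that is not known in advance. This stands, and the screen should stay. Calorie restriction begins at week 2 (section A, Dietary intervention), so a rise that starts then is plausible. For that shape the interaction test at p < 0.05 beats the weeks 4 to 16 contrast. For an effect confined to day 3 through week 2, that contrast has no expected signal, while the screen can still detect it.

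It can also be said that direction is not wholly lost, because the fitted interaction terms have signs and clustering displays patterns. This is true as description. But neither is a pre-specified estimate, and the clustering covers only taxa that have passed the screen.

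Third, Akkermansia is one element of a broader hypothesis about composition, which Adonis tests. It is not declared an endpoint; the primary clinical endpoint in section B is weight loss. This stands too, and it limits the weight of the point. Section D also refers to a Research Plan that is not among the documents, so a targeted analysis could be described there.

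A reader might infer that the plan gives away most of its power for Akkermansia, or that a real sustained rise would probably be missed. The documents do not support either. They give no effect size, dispersion, number of taxa or expected discovery rate. Some sustained rises favour the planned test, and large effects lose less: where a matched contrast has 99% power, the 10-df test keeps 86% at p < 0.05 and 68% at p < 0.01.

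**Conclusion.** The point holds on the text alone, without any power figure. The plan makes one taxon-specific, directional prediction and contains no test whose result would confirm or refute it. A significant screen would not show an increase, and whether Akkermansia passes depends partly on unrelated taxa.

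The power loss is conditional. For a moderate rise sustained from the first days, 80% for the targeted contrast corresponds to about 47%, 18% and 8% for the screen at p < 0.05, 0.005 and 0.001. These figures rest on categorical time, compound symmetry, complete data, a model that accounts for participant (the listed model terms include none) and assumed false-discovery cut-offs. For delayed or ramping effects the screen at p < 0.05 is the more powerful of the two.

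The screen is a reasonable exploratory tool. The gap should be closed before analysis, but it does not invalidate the microbiome plan.

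**What to change.** Add one pre-specified analysis to section C: the high minus normal protein difference in log abundance of Akkermansia, averaged over weeks 4 to 16 relative to baseline. Account for participant, use 1 df at two-sided 0.05, and report it with its direction and 95% confidence interval, outside the false-discovery family. State the assumed effect and SD, so that its power can be judged.

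Keep the interaction test with q-values for all taxa, including Akkermansia, to describe kinetics.

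The cost is a short addition to the SAP and one contrast from samples already planned, with no extra visits or participants. There are two downsides. It adds one test at 0.05. And the averaged contrast is less sensitive to early-only, brief, delayed or ramping effects, which is why Akkermansia should also stay in the screen.

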1. Venipuncture - There may be some discomfort associated with obtaining peripheral blood. Rarely, venipuncture may result in the development of a hematoma. Venipuncture will be performed by a certified phlebotomist in the VA's Laboratory Medicine department.
2. Stool collection - This will be done privately by the study patients in their homes using materials provided to them by the study coordinator. There are no risks associated with self-stool collection.
3. Confidentiality - Aspects of the subjects' medical history will be obtained by the study personnel. All data will be retained within the VA's electronic firewall to ensure the greatest confidentiality.

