 - 2. Life-threatening adverse event – A life-threatening adverse event is defined as any adverse experience that places the subject, in the view of the investigator, at immediate risk of death from the reaction as it occurred, i.e., it does not include a reaction that, had it occurred in a more severe form, might have caused death.
 - 3. Association with the use of study product (high or normal protein calorie restriction diets) – Association with the use of the study product means that there is a reasonable possibility that the adverse event may have been caused by the product under investigation. All adverse events are graded with regard to their association with the use of the study product. The classifications used include Not Related, Unlikely Related, Probably Related and Definitely Related.
 - 4. Unexpected adverse event – An unexpected adverse event is any adverse product experience that is not consistent with the current nutritional product insert in specificity or severity.
 - 5. Adverse event reporting procedure – The PI must report the occurrence of any serious adverse events, regardless of relationship to study product, or the first occurrence of any unexpected or previously unknown clinical event (regardless of Grade). A written report (Report for Serious/Life Threatening Events) of the event must be faxed within 5 working days to The VA GLAHS Institutional Review Board.

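### The high protein arm is supplied with pea protein, but no eligibility criterion excludes a candidate with known pea or legume allergy

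*Combined protocol and SAP*

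**What the plan says.** Section A, Dietary intervention, sets protein at 30% of calories in the high protein diet (HPD) and 15% in the normal protein diet (NPD). It then says: "Pea-based protein supplements will be provided to the HPD group to achieve the target of 30% calories from protein". No supplement is described for NPD.

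The exclusion list in Section A covers recent weight change, earlier weight loss, earlier calorie restriction, investigational drugs and laboratory values. It ends with "consumption of more than 1 alcoholic beverage per day, pregnancy or intention to become pregnant". D.1.a repeats the list and ties it to referral: "They will be referred for study enrollment if they meet the inclusion criteria and do not meet any provisions of the exclusion criteria".

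Under Enrollment and randomization, "medical history, current medications, smoking and alcohol history will be obtained by the study coordinator during the screening visit".

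On risk, D.1.a says: "Both dietary interventions are consistent with clinical practice for management of obesity and do not pose any appreciable risk to the patient". D.1.c then lists venipuncture ("There may be some discomfort associated with obtaining peripheral blood"), stool collection and confidentiality. D.2.b gives protections for the same three.

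**The concern.** A known food allergy can be found with one question before anyone is exposed. The plan hands one arm a product made from a specific legume, yet none of its eligibility rules acts on an allergy to it. The protocol does think about ingestion hazards elsewhere: D.2.b has participants warned against drinking the ethanol in the specimen cups. It gives no matching caution for the one product that participants are meant to eat.

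At stake is avoidable exposure of an individual. There is a smaller consequence for trial conduct. If an allergy comes to light only after assignment, any resulting withdrawal or non-adherence occurs in HPD alone. If it is settled before randomisation, both arms are drawn from the same population.

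**Working it through.** The plan states no figure on this point, so the check is mainly a reading of the text.

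1. **Who is offered the supplement.** Section A plans 216 participants at 1:1, so 216 / 2 = 108 in HPD. An eligible candidate has a 1/2 chance of that arm. The HPD composition is followed for 2 + 14 = 16 weeks.

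2. **Exclusion criteria.** Counted in Section A: (1) recent weight change, (2) earlier weight loss, (3) earlier calorie restriction, (4) investigational drugs, (5) laboratory values, (6) alcohol, (7) pregnancy or planned pregnancy. That is seven, and none concerns allergy. The list in D.1.a has the same seven.

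3. **Inclusion criteria.** Both lists deal with age, BMI and smoking habits. Section A also permits prescription medication that is not for obesity. Neither list makes tolerance of the study foods a condition of entry.

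4. **Fallback.** No clause gives the investigator discretion to exclude. Medical history is collected at screening, but no specific allergy question is named and no criterion uses an allergy found there.

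5. **Risk sections.** D.1.c lists three risks, none of them the supplement, and D.2.b covers the same three. D.1.a speaks only of the diets in general. The supplement is named only under Dietary intervention in Section A.

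6. **Putting these together.** A candidate who satisfies the age, BMI and smoking criteria, meets none of the seven exclusions and has a known pea allergy passes every written rule and can be randomised to HPD.

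7. **Effect on the comparison.** Each affected person in HPD is 1/108 = 0.9% of that arm. The documents give no allergy frequency. If few people are affected, which is an assumption, the effect on the difference in mean weight loss is negligible.

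**The case against.** The strongest reply is that several steps before exposure would probably catch a known allergy. Written consent is required before any study procedure or randomisation. If the form names the supplement, an allergic candidate can decline. The consent pages are not in the public document, so this cannot be judged either way. Medical history is also taken at screening, and the referral sentence in D.1.a does not oblige the investigator to randomise everyone referred. All of this stands, and it lowers the likelihood of harm. It does not supply a rule: a consent warning leaves the decision to the candidate, and medical history leads to no stated action on allergy.

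A second reply is that Section A says supplements are provided, not that they must be taken. No dose or required intake is given, and nothing forbids reaching 30% protein from other foods. This also stands. For that reason a reader might infer that anyone unable or unwilling to take the product should be excluded too, but the documents do not support going that far. Inability to take the product is a matter of acceptability, and it need not prevent a participant from following the diet.

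A third reply is that the plan monitors adverse events and grades each for association with the diets (Section E.c). That is correct, but monitoring acts only after exposure. A reader might go further and infer a reporting gap, because E.c.4 judges whether an event is expected by whether it is "not consistent with the current nutritional product insert in specificity or severity", and no such insert is identified. That does not follow. E.c.5 requires serious events to be reported regardless of relationship, and it also covers "the first occurrence of any unexpected or previously unknown clinical event (regardless of Grade". The insert is a separate drafting matter and forms no part of this point.

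**Conclusion.** The concern holds as a minor gap in individual safety. The written criteria admit a person with known pea or legume allergy to a one-in-two chance of the arm supplied with pea protein, and the listed risks do not name the product. This conclusion rests on the text of the eligibility and risk sections and needs no assumption about how common such allergy is.

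Two stronger readings are not supported. A reader might attach a probability that an allergic person is assigned to HPD, or is harmed. The documents give neither an allergy frequency nor a supplement dose, so any such figure would come from outside them; assignment to HPD is also not the same as exposure or harm. A reader might also infer that one-sided dropout would bias the weight-loss result. With each affected person making up 0.9% of the arm, and assuming few are affected, no endpoint, analysis or conclusion changes materially.

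**What to change.** Add known allergy to pea or other legumes to the exclusion criteria in Section A and to the repeated list in D.1.a. Ask every candidate about it at the screening visit and settle the answer before randomisation, whichever arm the candidate would receive, so that the rule applies equally to both groups. Add the pea supplement to the potential risks in D.1.c, with allergic reaction as the named risk.

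The cost is a protocol amendment with IRB review, one screening question and a few screen-outs. Some of those screened out would have been assigned NPD and would never have been offered the supplement. That is the price of keeping eligibility the same for both arms. Nothing in the statistical analysis needs to change.
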